2.3 BENEFIT - RISK ASSESSMENT

The treatment of patients with AML ≥ 65 years of age has become increasingly important as the age of population increases. Patients ≥ 65 years of age with previously untreated, relapsed or refractory AML have an overall poor prognosis with very limited treatment options. If patients are unfit for standard intensive treatment, the participation in a clinical trial would be the appropriate choice as recommended by clinical practice guidelines ([R15-5032](#)).

The most relevant side effect of decitabine administration is expected to be a transient inhibition of proliferation of normal dividing cells (e.g. in bone marrow). The effects on the hematopoietic system lead to a temporary decrease of blood cells (red cells, white blood cells and platelets). CD33 is not known to be expressed outside of the hematopoietic system. The anticipated side effect profile of BI 836858 based on the CD33 expression profile comprises predominantly hematologic adverse events such as neutropenia.

As the cardinal symptom of AML patients is cytopenia, the symptoms of AML and haematological side effects of treatment with BI 836858 and decitabine are expected to overlap. For most anti-leukemia therapy, a drug-related transient worsening of cytopenia is common and inevitable. Therefore, especially the CTCAE grade and duration of cytopenia (as well as complications of cytopenia) will be important safety criteria that will be closely monitored for clinical symptoms of infections throughout this trial in order to limit the risk of the treatment with the trial drugs used in combination in this trial. The use of anti-infective prophylaxis (refer to [Section 4.2.1](#)) is strongly recommended.

The preclinical safety assessments for BI 836858 have revealed TNF-alpha and INF-gamma release, suggesting a potential for infusion-related reactions. So far only clinical data from 20 patients with refractory/relapsed AML, treated with weekly 10 and 20 mg of BI 836858 in the ongoing first in human trial, are available. Infusion-related reaction (IRR) was the most frequent drug-related adverse event (AE), reported in 7 patients (35%). Considering these data and the experience with other monoclonal antibodies in hemato-oncology indications, infusion-related reactions are likely. Prophylactic measures will be recommended for primary prevention, and supportive treatments are available (see [Section 4.1.4](#)).

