4.1.4.2 Re-treatment criteria

Patients will be treated in repeat cycles in the absence of permanent treatment discontinuation criteria according to [Section 3.3.4.1](#).

Before the start of a subsequent cycle, adverse events and safety laboratory will be assessed. To continue treatment with further administrations of any of the two trial drugs, all of the following criteria must be met (depending on the disease status only criterion 1 or 2 is applicable):

- 1) **For patients with circulating blasts or persistent marrow disease ($\geq 5\%$ BM blasts; evidence of active leukemia):** Treatment shall proceed as per the initially allocated treatment group regardless of pre-treatment neutrophils.
 - a. Patients with active leukemia with grade 4 thrombocytopenia (platelets $< 25,000/\mu\text{L}$) may continue on trial treatment as allocated provided that there is no evidence of bleeding and post-transfusion platelet count is at least 25,000/ μL .
 - b. Patients with pre-existing (prior to study entry) grade 3 or 4 neutropenia or grade 3 or 4 thrombocytopenia will continue with therapy in the absence of fever ($\geq 38.5^\circ\text{C}$) and/or uncontrolled infection as prescribed. However, patients allocated to the intensive decitabine treatment schedule (10 consecutive days) with pre-existing grade 2 (or better) neutropenia or thrombocytopenia who have grade 4 neutropenia or thrombocytopenia shall be cut to the standard decitabine treatment schedule (5 consecutive days) for future cycles (EXCEPT for patients with absolute blasts count $> 5000/\mu\text{L}$ who may be eligible to continue with the intensive decitabine treatment (10 consecutive days) and should be discussed with the TCM and/or the Coordinating Investigator).

2) **For patients with no evidence of disease in blood or marrow (< 5% BM blasts):**
After completion of the first on-trial treatment cycle, the initially allocated treatment shall proceed regardless of neutropenia or thrombocytopenia. However, patients must be transfused to $\geq 25,000/\mu\text{L}$ platelets prior to administration of next treatment (including weekly administrations of BI 836858 therapy, if applicable).

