- For subsequent cycles, patients with pre-existing grade 4 neutropenia shall proceed with treatment in the absence of ongoing fever or uncontrolled infection. However, patients with pre-existing grade 2 (or better) neutropenia who have grade 4 neutropenia (neutrophils $< 500/\mu\text{L}$) should have all treatment(s) held for 2 weeks and then discussed with the TCM and/or the Coordinating Investigator if grade 4 neutropenia persists. Patients without evidence of fever or uncontrolled infection may be eligible to continue with treatment as allocated.
- Patients with grade 4 thrombocytopenia may continue on allocated trial treatment provided that post-transfusion platelet count is at least $25,000/\mu\text{L}$, but patients with pre-existing grade 2 (or better) thrombocytopenia should have treatment held for 2 weeks and then discussed with the TCM and/or the Coordinating Investigator if grade 4 thrombocytopenia persists. Patients without evidence of bleeding may be eligible to continue therapy provided the patient can be transfused to $\geq 25,000/\mu\text{L}$.

3) Acceptable tolerability (in case of a drug related AE at the planned start of a further administration, patients may continue therapy only after recovery to a level which would allow further therapy, i.e. CTCAE grade 1 or baseline value). Patients who do not meet these criteria for further therapy should be discussed with the TCM and/or the Coordinating Investigator and may be eligible to continue if the toxicity is not clinically significant.

In case criterion 1 and 3 (or criterion 2 and 3) are not fulfilled, blood counts and/or the adverse events should be re-evaluated at least weekly.

Subsequent cycles can be delayed up to 2 weeks to meet the above criteria. Longer delays should be discussed with the Coordinating Investigator. Patients with delays longer than 8 weeks due to a drug-related event (e.g. delay in recovery of blood counts or awaiting resolution of toxicity) will be withdrawn from study.

All of the above re-treatment criteria apply when a subsequent cycle is started, i.e. this is applicable for combination treatment in both parts of Phase I, for combination treatment in Arm 1 of the Phase II part, and also for the start of a new cycle with decitabine monotherapy in Arm 2 of Phase II.

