5.3.1 Dose limiting toxicity (DLT)

DLT is defined as any non-disease-related non-hematological AE of CTCAE grade 3 or higher.

Expected non-hematological disease-related AEs will not be regarded as a DLT. These include complications resulting from hematological AEs such as:

- Bleeding and complications from bleeding due to thrombocytopenia as defined by the Investigator
- Infection and complications from infections due to neutropenia as defined by the Investigator
- Constitutional symptoms due to anaemia as defined by the Investigator

Infusion-related reactions (IRR) associated with the administration of BI 836858 should be reported as Adverse Event of Special Interest (AESI, refer to [Section 5.3.8.1](#)), but will not be regarded as a DLT. The exception is anaphylaxis which occurs despite premedication with glucocorticoid or which does not resolve with glucocorticoid (i.e. such cases of anaphylaxis will be regarded as a DLT).

Patients who do not receive at least 3 administrations of BI 836858 due to BI 836858-related toxicity are considered to have developed a DLT. If Cycle 2 is not started until 57th day from Day 1 of Cycle 1 as a result of drug-related AE, this AE is considered as DLT (i.e. treatment delay of \geq 4 weeks of the start of Cycle 2 due to drug-related AE). Patients who do not experience a DLT but do not receive all 3 planned administrations of BI 836858 during Cycle 1 for reasons other than toxicity or tolerability will not be evaluable for DLT and cannot be used to establish the MTD.

Infection will not constitute a DLT unless it is felt that the infection resulted from unexpectedly complicated myelosuppression; degree of severity and/or duration as assessed by the Investigator.

Since patients with refractory leukemia have infections and bleeding complications from myelosuppression, these events will not be considered as DLT unless they occur in the setting of prolonged myelosuppression from the combination treatment. Prolonged myelosuppression is defined as ANC < 1000/ μ L and PLT < 100,000/ μ L by day 56 of Cycle 1 in the setting of bone marrow showing < 5% blasts, without evidence of persistent cytogenetic abnormalities or minimal residual disease by flow cytometry. In case persistent cytogenetic abnormalities or immunophenotypic evidence of leukemia is present, myelosuppression would be considered secondary to leukemia even if morphology shows < 5% blasts.

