5. ENDPOINTS(S)

5.1 PRIMARY ENDPOINT(S)

Phase I

The primary endpoints in the Phase I part of the trial are the maximum tolerated dose (MTD) and the number of subjects with of dose limiting toxicity (DLT) during the MTD evaluation period.

Maximum tolerated dose (MTD):

The MTD is defined as the highest dose of BI 836858 (in combination with decitabine) with less than 25% risk of the true DLT rate being above 33% during the MTD evaluation period.

MTD evaluation period:

The MTD evaluation period is defined as the time from the first administration of study drug to the start of the second treatment cycle or the end of 30-day residual effect period after last administration of study drug, whichever comes first. Subjects who were replaced during the MTD evaluation period will not be considered for MTD determination. The subjects who are completed the MTD evaluation period without being replaced are considered MTD evaluable.

In case a subject has not completed the required number of administrations due to BI 836858 related toxicity, he/she will not be replaced and this will be considered as DLT. However, subjects who have not completed the required number of administrations of BI 836858 for reasons other than BI 836858 related toxicity will be replaced. Subjects who were replaced during the MTD evaluation period will not be considered for MTD

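### For patients re-treated on Day 29, the Day 56 myelosuppression condition in the DLT definition cannot be met within the primary-endpoint window, and the re-treatment criteria conflict on whether such patients should be held

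*Protocol*

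**What the plan says.** Four places bear on this point.

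- **Protocol 4.1.4.2, criterion 2** covers patients with under 5% marrow blasts: "After completion of the first on-trial treatment cycle, the initially allocated treatment shall proceed regardless of neutropenia or thrombocytopenia". Platelets need only be transfused to 25,000/µL. The two-week holds for grade 4 cytopenia sit in the bullets that follow, the first of which opens: "For subsequent cycles, patients with pre-existing grade 4 neutropenia shall proceed with treatment in the absence of ongoing fever or uncontrolled infection".
- **Protocol 4.1.4.2, criterion 3** applies on top of criterion 1 or 2, because "all of the following criteria must be met". Where a drug-related adverse event is present, "patients may continue therapy only after recovery to a level which would allow further therapy, i.e. CTCAE grade 1 or baseline value". Blood counts are not exempted. A patient who falls short may still continue after discussion if the toxicity is not clinically significant.
- **Protocol 5.3.1** says of infection and bleeding from myelosuppression that "these events will not be considered as DLT unless they occur in the setting of prolonged myelosuppression from the combination treatment". That setting means ANC below 1000/µL and platelets below 100,000/µL "by day 56 of Cycle 1 in the setting of bone marrow showing < 5% blasts", with no cytogenetic or flow evidence of leukaemia.
- **SAP 5.1** (repeated in 6.1 and 7.4) fixes the window for the primary endpoint: "The MTD evaluation period is defined as the time from the first administration of study drug to the start of the second treatment cycle", or to the end of the 30-day residual effect period if that comes first.

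**The concern.** The MTD and the number of patients with DLT are the Phase I primary endpoints. Section 5.3.1 makes one class of DLT depend on blood counts by Day 56 of Cycle 1, and only in patients whose marrow has cleared. Criterion 2 sends those same patients into Cycle 2 without regard to counts, and the SAP stops looking when Cycle 2 starts. For a patient handled that way, the rule cannot operate.

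The error would run one way, towards fewer DLTs. It also concerns the toxicity the protocol most expects: "The anticipated side effect profile of BI 836858 based on the CD33 expression profile comprises predominantly hematologic adverse events such as neutropenia". The same section calls the grade and duration of cytopenia important safety criteria. The exposed case is a serious thrombocytopenic bleed in a leukaemia-free patient who received all three Cycle 1 administrations and started Cycle 2 on time.

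**Working it through.** **Inputs.** Earliest Cycle 2 start, Day 29 (Flow Chart footnote). Day 57 delay rule and Day 56 condition (5.3.1). Two-week hold and 8-week limit on delay (4.1.4.2). MTD evaluation period (SAP 5.1). Overdose probabilities (Table 10.2:1). Priors (Table 7.1.1:3).

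**Step 1: the plan's own figure.** Section 5.3.1 equates a Cycle 2 start on Day 57 with a delay of at least 4 weeks. 57 − 29 = 28 days = 4 weeks. This agrees, and it confirms that Day 29 is the reference for an undelayed start.

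**Step 2: where Day 56 falls under each reading of 4.1.4.2.**

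| Rule followed for Cycle 2 | Cycle 2 start | Day 56 inside the SAP window? |
|---|---|---|
| Criterion 2 alone | Day 29 | No. 56 − 29 + 1 = Day 28 of Cycle 2 |
| Two-week hold, if read as covering Cycle 2 | 29 + 14 = Day 43, unless extended after discussion | No. 56 − 43 = 13 days short |
| Criterion 3, up to the 8-week limit | up to 29 + 56 = Day 85 | Yes, if the hold passes Day 56 |

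The two-week hold also uses a different threshold. It concerns grade 4 cytopenia (neutrophils below 500/µL, platelets below 25,000/µL) in patients who began at grade 2 or better. A patient with ANC 700/µL and platelets 60,000/µL is within the count limits of 5.3.1 but is not held by those bullets.

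If Day 56 is read as a calendar day whatever the Cycle 2 start, the counts then reflect a second decitabine course, and the day is still outside the SAP window. Patients who never start Cycle 2 are a separate matter and not part of this point.

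**Step 3: what an uncounted DLT does to the model.** All rows assume 0/3 DLTs at 20 mg. The re-run used the 7.1.1 model with the Table 7.1.1:3 priors, 4 million Monte Carlo draws and likelihood weighting.

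| DLTs at 40 mg (scenario) | P(overdose) at 40 mg: plan / re-run | Next dose in Table 10.2:1, with P(overdose): plan / re-run |
|---|---|---|
| 2/3 (6) | 0.291 / 0.285 | 20 mg, 0.161 / 0.160 |
| 1/3 (5) | 0.103 / 0.103 | 80 mg, 0.244 / 0.259 |
| 0/3 (4) | 0.027 / 0.026 | 80 mg, 0.111 / 0.110 |

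Recording 2/3 as 1/3 takes 40 mg from above the 0.25 overdose limit to well below it. The plan's table then also allows 80 mg. The re-run puts 80 mg at 0.259, just over the limit. The gap of 0.015 is within what prior rounding and simulation error can produce, so permission for 80 mg in scenario 5 is borderline. The change from stepping down to at least remaining at 40 mg appears in both calculations. Recording 1/3 as 0/3 leaves the permitted next dose at 80 mg in the plan's table, so not every missed event would change a decision.

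**The case against.** A reader might infer that the myelosuppression route to DLT is closed altogether and that marrow toxicity has dropped out of the primary endpoint. The documents do not support that.

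- **Cycle 2 can be held.** The criteria are cumulative, and criterion 3 can hold a drug-related cytopenia. Sections 3.3.4.1 and 4.1.4.2 name slow count recovery as a cause of long delay. Section 4.1.4.3 requires delay when the criteria are not met on Day 29, which is the earliest start and not a mandated one. Section 4.1.4.2 also uses the term subsequent cycle for any new cycle, so the hold bullets might be read as covering Cycle 2.
- **Other DLT routes remain.** These are fewer than three administrations because of BI 836858-related toxicity, Cycle 2 not started until Day 57 because of a drug-related event, and infection judged to result from unexpectedly complicated myelosuppression. Low platelets, fever or uncontrolled infection can block the Day 16 and Day 23 doses, so marrow toxicity can feed the first of these.
- **The DLT is non-haematological by design.** Prolonged myelosuppression is not itself a DLT. It only qualifies infections and bleeds.
- **Later DLTs are used.** Protocol 5.3.2 and 7.3.1 re-run the model with DLTs from all cycles, and SAP 7.4 summarises DLTs over the on-treatment period and considers later ones for the recommended dose.

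All of this stands, and it limits the claim to possible under-counting. It does not remove the conflict. Criteria 2 and 3 point in opposite directions for a drug-related cytopenia, so whether the Day 56 condition can be observed depends on which sentence a site follows. The judged route covers infection, not bleeding. The all-cycle estimate takes only events that already constitute a DLT, and the qualifying condition stays tied to Day 56 of Cycle 1. It is therefore a partial safeguard.

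**Conclusion.** Protocol 4.1.4.2 criteria 2 and 3, Protocol 5.3.1 and the SAP's MTD evaluation period are inconsistent. For a patient with a cleared marrow who is re-treated on Day 29 under criterion 2, the condition that turns a bleed or infection into a DLT cannot be met within the primary endpoint. DLTs, chiefly thrombocytopenic bleeds, may be under-counted, and any such error lowers the count.

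The number of patients affected is not given and cannot be derived. The Phase I total of 49 (16 + 33) is not the right denominator, because it includes patients with persistent leukaemia, to whom the condition does not apply. The shift from 0.291 to 0.103 shows scale only. It assumes one three-patient cohort with one DLT missed, and is not an estimate for this trial.

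A reader might also infer that the selected dose was too high. The documents do not show that any such event occurred. Recruitment has ended and Phase II is cancelled, so what is at stake is the reported DLT count and the MTD conclusion, not dose assignment.

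**What to change.** **Reconcile the passages.** Bring 4.1.4.2 criteria 2 and 3, 5.3.1 and the SAP's MTD evaluation period into agreement, so that the stated condition can be assessed in the patients to whom it applies. Which clinical rule should prevail is for the sponsor and investigators. This review takes no position.

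**Add a labelled sensitivity analysis to SAP 7.4.**

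- Population: MTD-evaluable patients with under 5% marrow blasts, and no known cytogenetic or flow evidence of leukaemia where available, who started Cycle 2 before Day 56 with ANC below 1000/µL and platelets below 100,000/µL.
- Events: grade 3 or higher infections and bleeds from Cycle 1 Day 1 to Day 56, whenever Cycle 2 began.
- Display: a column beside the DLT count, plus one further BLRM run with these events counted as DLTs. The primary run stays unchanged.

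It must be labelled as sensitivity because it departs from 5.3.1: counts are taken at Cycle 2 start rather than Day 56, and the cytogenetic and flow condition is applied only where data exist. Phase I does not mandate cytogenetic testing, so the full definition may not be recoverable.

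**Cost.** One reconciling sentence, one column and one model run, using counts, marrow results and adverse events already scheduled for Cycles 1 and 2. Events after Cycle 2 starts are confounded by the second course, some may reflect expected decitabine cytopenia, and the sensitivity DLT rate may rise.

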One of the recommended treatment regimens for decitabine is continuous i.v. infusion over 1 h repeated daily for 5 days, but more intensive treatment regimen starting with repeated i.v. infusions daily for 10 days for the first few cycles, followed by individually customized therapy in subsequent cycles is also widely used. The intention of this more intensive, but individually customized treatment based on response and toxicity, is to improve tolerability and response.

Repeated cycles of decitabine are given every 4 weeks, irrespective of the duration of the decitabine administration (i.e. consecutive Days 1-5 or Days 1-10 of each cycle), in order to allow efficient incorporation of drug into the newly synthesized DNA of myeloid blast. Most common adverse reactions of decitabine ($> 50\%$) are neutropenia, thrombocytopenia, anaemia, and pyrexia. Other common adverse events include nausea, vomiting, diarrhoea, constipation, fever, oedema, hyperglycemia, hypomagnesemia, hypokalemia, arthralgias, back pain, cough, headache, insomnia, rash, petechiae, and pallor ([R11-1101](#), [R11-1104](#)). For detailed efficacy, safety, and pharmacology profile information of decitabine, refer to the EU Summary of Product Characteristics (SPC) for decitabine ([R15-4802](#)). Detailed information on this medicinal product is available on the website of the European Medicines Agency (EMA) website www.ema.europa.eu.

Also, in patients ≥ 65 years of age with previously untreated AML, who were ineligible for intensive therapy, decitabine has been investigated. Recently, the trial results from a Phase III

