All withdrawals will be documented and the reason for withdrawal recorded. As soon as a patient is withdrawn from the trial treatment, the End of Treatment (EOT) visit and the End of Residual Effect Period (REP) visit (EoR visit) have to be performed if feasible. Every effort should be made to follow-up with patients in case an adverse event (AE) is still ongoing at the time of withdrawal. If a patient is withdrawn from the trial due to documented full consent withdrawal (i.e. withdrawal from both, trial treatment and trial participation), no further visits will be completed and no further trial data will be collected. However, if

information about survival status is publicly available, then the Investigator is requested to report this information in the eCRF.

A patient has to discontinue trial drug administration, i.e. both BI 836858 and decitabine, in case:

- a DLT occurs which does not recover to a degree that allows treatment continuation (see [Section 4.1.4](#)).
- development of progressive disease (PD) or any other concomitant diagnosis including deterioration of general condition develops resulting in an indication to start any other therapy for AML.

Patients who have not completed at least 3 administrations of BI 836858 during cycle 1 due to BI 836858-related toxicity will not be replaced; this will be considered as a DLT. However, patients who have not completed at least 3 administrations (1 cycle) of BI 836858 for reasons other than BI 836858-related toxicity will be replaced.

Patients who experienced DLT but have subsequently recovered and are able to resume trial treatment will be allowed to continue on trial treatment, as long as criteria for further treatment are met ([Section 4.1.4.1](#)).

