Furthermore, the re-treatment criteria absence of fever ($\geq 38.5^\circ\text{C}$) and/or uncontrolled infection and platelets $\geq 25,000/\mu\text{L}$ apply for the weekly administrations of BI 836858 after Day 1 of any given cycle, (i.e. Day 16 and Day 23 of Cycle 1 and Day 8, Day 15 and Day 22 of any further cycle).

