7.2 NULL AND ALTERNATIVE HYPOTHESES

The analyses in this trial are descriptive and exploratory. No formal statistical tests will be performed.

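### The protocol and SAP disagree on whether a patient with fewer than 3 Cycle 1 administrations, because of toxicity not related to BI 836858, counts in the MTD analysis

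*Protocol*

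**What the plan says.** Cycle 1 has at most 3 administrations of BI 836858 (protocol Flow Chart), and all 3 are needed. Under Section 4.1.4.2 the fever, uncontrolled-infection and platelet criteria "apply for the weekly administrations of BI 836858 after Day 1 of any given cycle, (i.e. Day 16 and Day 23 of Cycle 1". One infusion that is withheld and not given later therefore brings the under-dosing rules into play. Those rules stand in four places:

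- **Protocol 5.3.1, DLT limb:** "Patients who do not receive at least 3 administrations of BI 836858 due to BI 836858-related toxicity are considered to have developed a DLT".
- **Protocol 5.3.1, evaluability limb:** patients without a DLT who miss any of the 3 administrations "for reasons other than toxicity or tolerability will not be evaluable for DLT and cannot be used to establish the MTD".
- **Protocol 3.3.4.1:** too few administrations because of BI 836858-related toxicity is a DLT and the patient is not replaced. Patients with too few "for reasons other than BI 836858-related toxicity will be replaced".
- **SAP 5.1, 6.3 and 7.4:** SAP 5.1 makes the same split as protocol 3.3.4.1 but refers only to a required number, which it does not give. Replaced subjects are left out of the MTD determination (5.1, 7.4). The MTD evaluable set in 6.3 sets its threshold at 2 doses.

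**The concern.** Take a patient whose Day 16 or Day 23 infusion is not given because of fever or infection that the investigator attributes to decitabine, and who has no DLT. Attribution is settled, so the documents should give one answer. They do not. Under protocol 3.3.4.1 and SAP 5.1 the reason is not BI 836858-related, so the patient is replaced and excluded. Under protocol 5.3.1 the reason is toxicity, so the exclusion for other reasons does not apply. The patient is neither a DLT nor non-evaluable, and stays in the binomial denominator as a DLT-free observation with incomplete exposure.

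The DLT count and its denominator are the only trial data that the Bayesian logistic regression model (BLRM) takes in. The choice therefore reaches the primary endpoint, the MTD and the doses that the overdose criterion permits.

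**Working it through.** **Step 1. The rules side by side**, for a patient with fewer than 3 Cycle 1 administrations and no other DLT:

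| Reason for the shortfall | Protocol 3.3.4.1, SAP 5.1 | Protocol 5.3.1 |
|---|---|---|
| BI 836858-related toxicity | DLT, not replaced | DLT |
| Toxicity not related to BI 836858 | Replaced, excluded | Neither DLT nor non-evaluable, so kept as DLT-free |
| Not toxicity or tolerability | Replaced, excluded | Not evaluable |

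Only the middle row conflicts. SAP 6.3 adds a separate mismatch. Read literally, its 2-dose threshold applies to patients stopped for BI 836858-related toxicity, so a patient stopped after one dose for that reason is a DLT under the protocol but outside the SAP's evaluable set.

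**Step 2. Reproduce the plan's own figures.** Section 7.2 states "No formal statistical tests will be performed", so there is no error rate to check; the effect runs through the BLRM. Inputs are the model of Section 7.1.1 and the priors of Table 7.1.1:3:

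- logit(π1) = log α1 + β1 log(d1/160); logit(π2) = log α2 + β2 log(d2/20)
- π0 = π1 + π2 − π1π2; odds(π12) = odds(π0) × exp(η × d1/160 × d2/20); DLTs binomial with probability π12
- overdose means π12 ≥ 0.33; a dose is permitted if P(overdose) < 0.25

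Four million prior draws were weighted by the binomial likelihood and compared with Table 10.2:1:

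| Data | Dose assessed | Refit | Printed |
|---|---|---|---|
| 20 mg 0/3 | 20 mg | 0.039 | 0.040 |
| 20 mg 1/3 | 40 mg | 0.226 | 0.222 |
| 20 mg 2/3 | 20 mg | 0.416 | 0.417 |
| 20 mg 0/3, 40 mg 1/3 | 80 mg | 0.259 | 0.244 |
| 20 mg 0/3, 40 mg 2/3 | 40 mg | 0.285 | 0.291 |

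The largest gap in this table is 0.259 − 0.244 = 0.015.

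**Step 3. One under-dosed patient at 20 mg, with one DLT in another patient of the cohort:**

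- Kept as DLT-free, 1/3: P(overdose) at 40 mg is 0.222 printed (0.226 refit). 40 mg is permitted.
- Excluded, not yet replaced, 1/2: 0.295 (refit). 40 mg is not permitted. The margin over the limit is 0.295 − 0.25 = 0.045, three times the largest gap above.
- Excluded, replaced by a DLT-free patient: 1/3 again, 40 mg permitted.
- Excluded, replaced by a patient with a DLT: 2/3. Table 10.2:1 permits no dose.

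With no other DLT at 20 mg, nothing changes: P(overdose) at 40 mg is 0.077 for 0/3 (printed 0.076) and 0.101 for 0/2, both permitted. With 0/3 at 20 mg and one other DLT at 40 mg, keeping gives 0.244 printed at 80 mg and excluding gives 0.307. This example is weaker, because the refit of the first figure (0.259) falls on the other side of the limit.

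**Step 4. Direction of the bias.** Suppose two of three patients are fully exposed with true DLT rate p, and the third is under-dosed and kept as DLT-free. The expected DLT fraction is (2p + 0)/3 = 2p/3, against p with a fully exposed replacement. At the ends of the target interval, p = 0.16 gives 0.107 and p = 0.33 gives 0.22.

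**The case against.** **Intent is clear elsewhere.** Sections 3.1 and 4.1.3.1, in the rule for escalating on two patients, describe a countable DLT-free patient as one dosed at least three times and followed to the end of Cycle 1. The rationale for the Section 5.3.1 sentence in the amendment log says the same. This stands as evidence of which reading was meant, but it changes neither the wording of 5.3.1 nor the 2-dose set in SAP 6.3.

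**The 1/2 state is temporary.** Escalation on two patients is allowed only if neither had a DLT, so at 1/2 the committee would wait for a third. That stands. During escalation, the practical difference is a real third observation instead of an assumed zero.

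**Recruitment has ended.** True, so nobody can now be replaced. SAP 7.4 still has to flag each treated patient for DLT and for MTD evaluability, and a patient excluded but never replaced leaves a smaller denominator.

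A reader might infer more than the documents support:

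- *That DLT versus replaced has no rule.* It has one, BI 836858-relatedness, stated alike in protocol 3.3.4.1 and 5.3.1 and SAP 5.1. Section 2.3 expects the effects of AML and both drugs to overlap, so attribution is hard, but that is not a missing rule.
- *That 5.3.1 contradicts itself*, because it exempts "Infection and complications from infections due to neutropenia as defined by the Investigator" while a dose missed for such an event can be a DLT. An exempt event and a separate missed-dose limb can coexist. The text does not say whether that is intended.
- *That the path is common.* Section 1.2.2 lists neutropenia, thrombocytopenia and pyrexia among the "Most common adverse reactions of decitabine", each above 50%, but gives no timing and no rate of missed Cycle 1 infusions.
- *That low platelets force a missed dose.* Section 4.1.4.2 provides for transfusion "prior to administration of next treatment (including weekly administrations of BI 836858 therapy, if applicable", and Section 4.1.4 allows up to 10 days between infusions. The missed-dose wording in 4.1.4 also covers only cycles with BI 836858 given on Day 1, which Cycle 1 is not.

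**Conclusion.** The conflict is real but narrow. For fewer than 3 administrations because of toxicity not related to BI 836858, protocol 3.3.4.1 and SAP 5.1 exclude the patient and protocol 5.3.1 keeps the patient as DLT-free. The SAP adds an unstated number in 5.1 and a 2-dose threshold in 6.3.

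Keeping such patients lowers the estimated DLT rate. In the clearest case, one other DLT at 20 mg, the overdose probability at 40 mg is 0.222 if the patient is kept and about 0.295 if excluded and not replaced, on either side of the 0.25 limit. A DLT-free replacement removes the difference; without another DLT at 20 mg there is no change in the permitted dose.

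This rests on the Table 7.1.1:3 priors, which Section 7.1.1 allows to be updated, and on counting the Day 8/Day 9 split as one administration, as the Flow Chart maximum of 3 implies. The frequency cannot be estimated from the documents. It should be corrected because it defines the primary endpoint's denominator.

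**What to change.** 1. Reconcile the evaluability sentence in protocol 5.3.1 with protocol 3.3.4.1 and SAP 5.1, so that one rule covers toxicity not related to BI 836858. With recruitment closed, the SAP is the practical place to state it, before the flags in SAP 7.4 are set.
2. Give the required number of Cycle 1 administrations in SAP 5.1 and make SAP 6.3 agree with it and with the protocol. State that the split first dose is one administration.
3. List every treated patient with fewer than 3 Cycle 1 administrations, by dose, with the reason, the attribution and the resulting flags.
4. State whether an infusion missed for an event that 5.3.1 exempts, but that is attributed to BI 836858, counts under the missed-dose DLT limb. The passages must be reconciled; no DLT rule is proposed here.

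The cost is wording in two documents and one listing from data already collected. The downside is possibly a few fewer evaluable patients. When an infusion is withheld does not change.
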